8.3.4.1.3. Adverse Event seriousness assessment

The Investigator will evaluate the seriousness of any event as per the definition (§ 8.3.1).

8.3.4.2. By the Sponsor

The Sponsor will also evaluate the seriousness of all events which are reported to him by the Investigator, and the causality of the study drug and any other treatments for each AE.

AEs for which the Investigator or the Sponsor consider that a causal link with the study product could reasonably be envisaged will be considered to be suspected adverse effects. Should the evaluations of the Sponsor and the Investigator differ with regard to causality, then both will be reported in the declaration of suspected adverse effect.

The Sponsor is responsible for determining the expectedness of the serious adverse event, using the IMP reference safety information (see §8.3.2 above). Each SAE has to be classified by the sponsor as expected or unexpected for the IMP.

8.4. Procedures in place for the recording and notification of serious adverse events

The Investigator will notify the Sponsor without delay on the day of discovery of any SAEs.

The Investigator must:

- **note** in the participant's medical file the date on which he become aware of the SAE (at a follow-up visit or a telephone contact with the participant or a third person, etc);
- immediately inform (within 24 h of awareness of SAE by the Investigator) by telephone the Sponsor Medical responsible, and the Sponsor Clinical Project Manager, and confirmed by an email to [contact] (copy [contact])
- complete the SAE form and send it by email to [contact] (copy [contact]), immediately after of being informed of this event, without waiting for the results of the clinical outcome or of additional investigations, and in any case within 24 h of knowledge by the investigator; this form includes a description of the event, onset date and seriousness criteria, duration, severity, causal relationship to study drug, outcome, measures taken and all other relevant clinical and laboratory data;
- provide the persons designated above, as they become available, additional information (follow-up SAE form) with all relevant information (together with translation into English language) that could contribute to the clarification of the SAE and to the assessment of potential risk for the study subjects and with anonymised copies of the documents which provide additional useful

information, such as hospital admission reports, reports of further consultations, laboratory test reports, reports of other examinations aiding diagnosis (where possible, the results from pretreatment assessments should be appended for comparison with the results obtained under treatment), or the autopsy report, if autopsy is performed; any follow-up reports should be submitted as soon as possible, and if possible within 2 working days of knowledge, inform the persons designated above of the outcome, if not previously reported, and other relevant follow up information of the SAE as soon as possible;

The Investigator must also report all SAEs/SARs in the eCRF by filling in the AE form. Where the same data are collected in the eCRF and in the SAE form, the two forms must be completed in a consistent manner, and the same medical terminology should be used.

If the SAE is the reason of subject drop-out from the study, the Investigator will detail the reason for such a statement in the comment section of the form and the Sponsor Medical Responsible and Sponsor Clinical Project Manager will be informed immediately (within 24 h of the investigator becoming aware of the event) by telephone and email.

The minimum criteria to be reported are as follows:

- a suspected investigational medicinal product;
- an identifiable subject (at least study subject identification code number but no subject initials);
- an AE assessed as serious;
- an identifiable reporting source;

The outcome of the SAE shall be classified as following:

- recovered/resolved;
- recovering/resolving;
- recovered/resolved with sequelae;
- not recovered/not resolved;
- fatal;
- unknown.

Details should be given for the latter four categories.

The Sponsor is responsible for all declarations to Ethics Committee and Health Authorities. The Sponsor will answer to any request from the Competent Authority or Ethics Committee concerning such reactions.

The Sponsor will notify all Suspected Unexpected Serious Adverse Reaction (SUSAR) to the European Medicines Agency (EMA), the Competent Authorities (the "Agence Nationale de Sécurité du Médicament et des Produits de Santé" (ANSM)), and the Ethics Committee (CPP), the two latter having given their approval for the research to take place, in compliance with the applicable safety reporting requirements (see appendix II).

In addition, as this is a first-in-Human study, the Sponsor will notify all SAE (including SUSARs, expected SARs and unrelated serious events) immediately to the Health Authorities (ANSM), the Ethics Committee (CPP) and the regional Health Agency (ARS). All product administrations will then be stopped for all subjects, and the necessary immediate procedures will be implemented to ensure subject's safety. In this case, the Sponsor will add a complementary report to all 3 authorities within 8 days.

If the study is definitively stopped (anticipated cessation), EUROFINS OPTIMED will declare it to ANSM and CPP within 15 days after the decision is taken.

In case the decision is taken to continue the study, then an amendment must be submitted and agreed before the study is continued.

8.5. Type and duration of the follow-up of subjects after adverse events

All subjects experiencing an AE, independent of whether considered associated with the use of the IMP or not, have to be monitored until symptoms subside or normalize, until a satisfactory explanation of the observed changes is found or until the investigator considers it medically justifiable to terminate follow-up.

This may also last until after end of the clinical trial.

Resolution of such events is to be documented on the eCRF AE and SAE form.

If a follow-up is necessary, the investigator will decide if the subject has to be hospitalized in the phase I center or if ambulant control examinations are sufficient. For this purpose, control appointments are agreed with the subject. Should it turn out after his release that a follow-up examination is necessary, the subject is called by the investigator or a qualified representative. If the subject is not reached although several calls were made, a written information will be sent out. If the subject does not answer after a reasonable period of time, its duration depending among others on the nature of the finding, he will be considered "lost to follow-up". The sponsor is informed about the outcome of the follow-up.

Information on the results of the follow-up examinations are forwarded to the monitor and sponsor as soon as they are available.

8.6. Other safety issues not falling within the definition of SUSAR, and Urgent Safety measures

Events may occur during a clinical trial which do not fall within the definition of Suspect Unexpected Serious Adverse Reaction (SUSAR) and thus are not subject to the reporting requirements for SUSARs, even though they may be relevant in terms of subject safety. These events/observations are not to be reported as SUSARs, but they might require other action, such as urgent safety measures, substantial amendments, or early termination of the trial.

Examples of Safety issues other than SUSAR are:

- new facts related to the conduct of a trial or the development of an IMP likely to affect the safety of subjects, such as:
 - a serious adverse event which could be associated with the trial procedures and which could modify the conduct of the trial,
 - a significant hazard to the subject population such as lack of efficacy of an IMP used for the treatment of a life-threatening disease,
 - a major safety finding from a newly completed animal study (such as carcinogenicity),
 - a temporary halt of a trial for safety reasons if the trial is conducted with the same investigational medicinal products in another country by the same sponsor,
- recommendations of the Data Safety Monitoring Board (DSMB), if any, where relevant for the safety of subjects,
- in the case of advanced therapy investigational medicinal products, relevant safety information regarding the procurement or the donor.

For this study in healthy subjects, any SAR will be considered as a "new fact" and treated as such (see section 8.4).

The Sponsor will inform with no delay the concerned Competent Authority and the Ethics Committee of safety issues which might materially alter the current benefit-risk assessment of the IMP while not falling within the actions listed above.

In case of occurrence of any new facts relating to the conduct of the trial or the development of the IMP where the new fact is likely to affect the safety of the subjects, the Sponsor and the Investigator shall take appropriate *urgent safety measures* to protect the subjects against any immediate hazard. The Sponsor

Temp-UPC-853-C du 07/08/2017

shall forthwith inform the competent authorities of those new facts and the measures taken and shall ensure that the Ethics Committee is notified at the same time.

Urgent safety measures may be taken without prior notification to the national competent authority. However, the Sponsor must inform *ex post* the national competent authority and the Ethics Committee of the Member State concerned of the new facts, the measures taken and the plan for further action as soon as possible. The *ex post* notification of urgent safety measures is independent of the obligation to: notify substantial amendments, notify early termination of the trial, and notify serious adverse events and serious adverse reactions, as per current regulations.

8.7. Modalities for safety declarations to Authorities (ANSM, CPP, ARS)

The declaration to ANSM follows the requirements.

CPP and ARS, if applicable, are informed by email and receive the same documents as requested by ANSM (see appendix II).

All details on roles, responsibilities, processes for safety reporting to Authorities (ANSM, CPP, ARS) and relevant contact details will be identified in the study Safety Management Plan prior to study start.

8.8. Procedure in case of a pregnancy in a trial subject's partner

In the unlikely event that any trial subject's partner becomes or is found to be pregnant while trial subject is receiving the study treatment or within 10 days after last administration of the IMP, the investigator must submit the event in writing, on a "Pregnancy Surveillance form", to the Sponsor in an expedited manner, i.e. within 24 hours, with the same procedure and timelines as for SAEs (see paragraph 8.5). This must be done irrespective of whether an AE has occurred.

Subjects will be instructed that if their partner becomes pregnant during the study, this should be reported to the Investigator. The investigator should also be notified of pregnancy occurring during the study but confirmed after completion of the study.

The subject should try to convince his partner to come to the Clinical Unit and meet the Investigator. Consent will be sought from the partner by the Investigator.

Pregnancies that have been caused by the subject are recorded and tracked, if the partner has consented. The information submitted should include the anticipated date of delivery. The Investigator will evaluate the date of pregnancy start (1st day of last menstruation period) so that a potential exposure during pregnancy based on product's half-life could be evaluated.

The investigator will follow the trial subject's partner (once consent obtained from female partner) until completion of the pregnancy or until pregnancy termination (i.e., induced / spontaneous abortion). The investigator will provide pregnancy outcome information on a "Pregnancy Surveillance Form".

A pregnancy is not an SAE.

In the case of a live birth, a medically qualified person should assess the infant at the time of birth and submit a Child Surveillance form. An SAE should be declared in the case of unfavorable pregnancy outcome (abortion, still birth) or congenital abnormality (in addition to the Child Surveillance Form).

In case of in utero exposure, the parents will be proposed a follow-up of the new born up to the age of 2 years old.

In the case the consent of the partner would not be obtained, the pregnancy shall only be declared to the Sponsor without any information on the partner.

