- 14- Must agree to adhere to the contraception requirements defined in Section 4.3: use of condom by the male subject plus an effective method of contraception for the subject or the subject partner of child bearing potential from study drug administration until 90 days post-dosing OR use of a condom for 10 days post-dosing if the partner is known to be pregnant.

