4.3.2. Contraception requirements

Subjects who are sexually active must use, with their partner of child-bearing potential, a condom plus an approved method of effective contraception from the time of dosing to 90 days after study discharge. The following methods are acceptable:

- Partner's use of combined (oestrogen and progestogen-containing) hormonal contraception associated with inhibition of ovulation:
 - oral
 - intravaginal
 - transdermal
- Partner's use of progestogen-only hormonal contraception:
 - oral
 - injectable/implantable
 - intrauterine hormone-releasing system
- Partner's use of implantable intrauterine device
- Surgical sterilisation (for example, vasectomy or partner's bilateral tubal occlusion)

Alternatively, true abstinence is acceptable when it is in line with the subject's preferred and usual lifestyle. If a subject is usually not sexually active but becomes active, they, with their partner, must comply with the contraceptive requirements detailed above.

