When reporting an abnormal laboratory result as an AE, a clinical diagnosis should be recorded rather than the abnormal value itself, if available. However, in these cases, the AE should be recorded as the syndromic clinical diagnosis (e.g., acute pancreatitis instead of each finding separately: high levels of amylase, high levels of lipase, abdominal pain and vomiting; e.g. "hypokalemia" rather than "decreased potassium levels").

Temp-UPC-853-C du 07/08/2017

Adverse Drug Reaction (ADR),

All untoward and unintended responses to an IMP related to any dose administered i.e. any AEs judged by either the reporting Investigator or the Sponsor as having a reasonable possibility of a causal relationship with the IMP. This means that there are facts (evidence) or arguments to suggest a causal relationship between the event and the IMP (see definition of causality in 8.3.5.).

Serious Adverse Event or Reaction, a Serious Adverse Event (SAE) or Reaction (SAR) is any untoward medical occurrence or effect that at any dose:

- Results in death;
- Is life-threatening (at the time of the event): in this context refers to an AE in which the patient was at risk of death at the time of the AE; it does not refer to an AE that hypothetically might have caused death if more severe;
- Requires in patient hospitalization or prolongation of existing hospitalization: i.e. the AE requires at least an overnight admission or prolongs a hospitalisation beyond the expected length of stay;
- Results in persistent or significant disability or incapacity: i.e. the AE resulted in a substantial disruption of the subject's ability to conduct normal activities;
- Is a congenital anomaly or birth defect i.e. an AE outcome in a child or foetus of a subject exposed to the IMP before conception or during pregnancy;
- Is an important medical event: i.e., AE is medically significant: medical and scientific judgment should be exercised in deciding whether other situations should be considered serious events/reactions, such as important medical event that may not be immediately life-threatening or results in death or hospitalization but may jeopardize the subject or may require intervention to prevent one of the other outcomes listed in the above definition should also usually be considered as serious.
 - In addition, any suspected transmission via a medicinal product of an infectious agent is also considered a serious adverse event/reaction.

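### Section 8.8 asks subjects to report a partner pregnancy only if it occurs during the study, a period shorter than the protocol's own 10-day expedited window and 90-day contraception period (minor)

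*Protocol*

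**What the plan says.** Section 8.8 of the protocol sets two duties.

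- **Subject to investigator.** "Subjects will be instructed that if their partner becomes pregnant during the study, this should be reported to the Investigator". The sentence after it reads: "The investigator should also be notified of pregnancy occurring during the study but confirmed after completion of the study".
- **Investigator to sponsor, within 24 hours.** This applies if the partner becomes pregnant, or is found to be, "while trial subject is receiving the study treatment or within 10 days after last administration of the IMP".

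Two further sentences in 8.8 carry no dates: "Pregnancies that have been caused by the subject are recorded and tracked, if the partner has consented", and, where the partner does not consent, "the pregnancy shall only be declared to the Sponsor without any information on the partner". The definition of a serious adverse event in 8.3.1 also includes a congenital anomaly, described as "an AE outcome in a child or foetus of a subject exposed to the IMP before conception or during pregnancy", with no time limit.

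The precaution period is longer. Inclusion criterion 14 (section 4.1) requires contraception "from study drug administration until 90 days post-dosing". Section 4.3.2 requires it "from the time of dosing to 90 days after study discharge". Section 4.3.3 bars sperm donation for the length of the study and for 90 days after the dose. Section 4.3.1 requires condoms for 10 days because exposure through the ejaculate cannot be excluded, and bases the 10 days on more than 10 half-lives.

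The last visit is D4 for the 10 to 80 mg cohorts and D6 for the 160 to 500 mg cohorts (3.4.1). Later contact is arranged only for ongoing adverse events or abnormal laboratory results (3.4.2).

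**The concern.** The tracking, sponsor declaration and pregnancy follow-up in 8.8, and the pre-conception limb of the serious-event definition in 8.3.1, all depend on the site learning of the pregnancy. In this trial the source is the subject, so his instruction should run at least as long as the duties it feeds. As written, it appears to stop a few days after dosing.

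At stake is complete safety capture in a first-in-human trial. If contraception fails after the last visit, nothing in the protocol text prompts the subject to say so, and the outcome may be lost. The days between the last visit and day 10 matter most. The investigator then has a 24-hour duty, and the protocol itself still allows for drug in semen.

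**Working it through.** The protocol gives no figure for this, so the check compares its own time windows.

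**Step 1: what the study means for one subject.** Three places point to a short, per-subject meaning.
- Section 3.4.1 calls the D4 or D6 visit the end-of-study visit.
- The same section expects about 35 days per subject. Screening of up to 28 days plus D1 to D6 gives 28 + 6 = 34 days. A 90-day tail would give 28 + 90 = 118 days.
- Section 4.3.3 lists the length of the study separately from the 90 days after dosing, so the two are not the same period.

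**Step 2: convert to days after the dose.** The flow chart places T72h on D4 and T120h on D6.
- D4: 72 / 24 = 3 days.
- D6: 120 / 24 = 5 days.

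**Step 3: compare the windows.**

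| | D4 cohorts (10–80 mg) | D6 cohorts (160–500 mg) |
|---|---|---|
| Instruction ends, days after dose | 3 | 5 |
| Days to the end of the 10-day window | 10 − 3 = 7 | 10 − 5 = 5 |
| Days to day 90 (4.1) | 90 − 3 = 87 | 90 − 5 = 85 |
| Share of the 90 days | 87 / 90 = 97% | 85 / 90 = 94% |

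Under 4.3.2 the period runs 90 days from discharge, which the flow chart places on D4 for all cohorts, so to 3 + 90 = 93 days after the dose. The uncovered days are then 93 − 3 = 90 and 93 − 5 = 88. The choice of end date hardly changes the result. These are calendar days, not shares of risk.

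**Step 4: does the late-confirmation sentence help?** No. It allows late confirmation but still requires the pregnancy to have occurred during the study. It does not reach a later conception.

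**Step 5: is the 10-day window sound on its own terms?** Section 3.3.3.2 reports a geometric mean half-life of around 20 hours. Then 10 × 24 / 20 = 12 half-lives, which agrees with the basis stated in 4.3.1.

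**Step 6: what else could bring a report in?** The study card (5.1.2) gives subjects contact details. Section 8.3.3 records untoward events after completion as post-study events if the investigator reports them. Both are passive, and neither asks for pregnancies.

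**The case against.** The strongest reply is that pregnancy surveillance in 8.8 is tied to drug exposure. The start of pregnancy is dated so that exposure can be judged from the half-life, and the two-year child follow-up is for exposure in utero. By day 10 the drug is essentially gone. A precautionary contraception period may reasonably outlast an exposure-based surveillance window, and later reports would mostly concern pregnancies with no exposure. This largely stands for days 11 to 90. It does not cover the days from D4 or D6 to day 10, where the instruction is shorter than the exposure window itself. For the later days, 8.3.1 still makes some outcomes after pre-conception exposure reportable.

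A reader might also infer stronger points that the documents do not support:

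- **That the 10-day expedited window is too short.** It has a stated rationale, and Step 5 agrees with it.
- **That a conception on days 11 to 90 carries a recognised teratogenic risk.** Section 1.3 does not exclude teratogenicity or fetotoxicity, but it gives the lack of developmental animal data as the reason and points to measures against exposure through semen, which the first 10 days cover.
- **That a late pregnancy would be ignored.** The undated sentences in 8.8 and the definition in 8.3.1 apply once the site knows.
- **That subjects are never told.** The information leaflet and consent form were not available and may carry a longer instruction.
- **That a count of uncovered men can be given.** If the study is taken to end at the last subject's last visit (3.4.3), early cohorts would be covered and the last ones dosed would not. The protocol gives no cohort spacing, recruitment stopped from March to August 2020 (1.2.2), and some cohorts may not run (1.4). No number follows.

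**Conclusion.** The point holds as a minor inconsistency in the protocol text. The subject's instruction ends about 3 or 5 days after dosing. That is 7 or 5 days short of the investigator's own expedited window and about 87 or 85 days short of the 90-day precaution.

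This rests on reading the study as ending at the subject's last visit, which 3.4.1 and 4.3.3 favour but 8.8 does not state. It also concerns the protocol wording only.

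The practical risk is small. Each subject takes a single dose, genotoxicity tests were negative (1.2.1.5), and section 1.3 rates an effect of one dose on male fertility as very unlikely. Few pregnancies are to be expected among 64 men. No analysis and no escalation decision depends on it.

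**What to change.** In 8.8, and in what subjects are told at discharge, replace the limit to the study with a dated one: report any partner pregnancy conceived from dosing to the end of the contraception period, even if it is confirmed later. Keep the 24-hour route to the sponsor for conceptions within 10 days of dosing, and state a non-expedited report to the sponsor for later ones.

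The new sentence needs one end date, so 4.1 and 4.3.2 should be aligned (90 against 93 days after dosing, a clerical difference of 3 days). The same edit can correct the cross-reference in 8.8 for the serious-event procedure, which is in 8.4 and not 8.5.

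The cost is a few words in the protocol and the discharge instruction, plus perhaps a few late reports of pregnancies with no drug exposure. No visit or assessment is added.
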